### Immune-mediated Pericardial Disorders

Immune-mediated pericarditis should be suspected in any patient presenting with chest pain and may be associated with immune-mediated myocarditis (see section on myocarditis above).

Immune-mediated pericardial effusion and cardiac tamponade should be suspected in any patient presenting with chest pain associated with dyspnea or hemodynamic instability.

Patients should be evaluated for other causes of pericardial disorders such as infection (commonly viral), cancer related (metastatic disease or chest radiotherapy), cardiac injury related (post myocardial infarction or iatrogenic), and autoimmune disorders, and should be managed accordingly.

All patients with suspected pericardial disorders should be urgently evaluated by performing an ECG, chest X-ray, transthoracic echocardiogram, and cardiac MRI as appropriate per institutional guidelines. A cardiologist should be consulted. Pericardiocentesis should be considered for diagnostic or therapeutic purposes, if clinically indicated.

Patients with signs and symptoms of pericarditis, pericardial effusion, or cardiac tamponade, in the absence of an identified alternate etiology, should be treated according to the guidelines in the table below. Withhold treatment with atezolizumab for Grade 1 pericarditis and conduct a detailed cardiac evaluation to determine the etiology and manage accordingly.

Event	Management
Immune-mediated myocarditis, Grade 2–4	
 
• Permanently discontinue atezolizumab.
 
• Refer patient to cardiologist.
 
• Initiate treatment as per institutional guidelines and consider antiarrhythmic drugs, temporary pacemaker, ECMO, VAD, or pericardiocentesis as appropriate.
 
• Initiate treatment with corticosteroids equivalent to 1–2 mg/kg/day IV methylprednisolone and convert to 1–2 mg/kg/day oral prednisone or equivalent upon improvement.
 
• If event does not improve within 48 hours after initiating corticosteroids, consider adding an immunosuppressive agent.
 
• If event resolves to Grade 1 or better, taper corticosteroids over <math>\geq 1</math> month.
 

Immune-mediated pericardial disorders, Grade 2–4	

ECMO = extracorporeal membrane oxygenation; VAD = ventricular assist device.

#### Infusion-Related Reactions and Cytokine-Release Syndrome

No premedication is indicated for the administration of Cycle 1 of atezolizumab. However, patients who experience an infusion-related reaction (IRR) or cytokine-release syndrome (CRS) with atezolizumab may receive premedication with antihistamines, antipyretics, and/or analgesics (*e.g.*, acetaminophen) for subsequent infusions. Metamizole (dipyrone) is prohibited in treating atezolizumab-associated IRRs because of its potential for causing agranulocytosis.

IRRs are known to occur with the administration of monoclonal antibodies and have been reported with atezolizumab. These reactions, which are thought to be due to release of cytokines and/or other chemical mediators, occur within 24 hours of atezolizumab administration and are generally mild to moderate in severity.

CRS is defined as a supraphysiologic response following administration of any immune therapy that results in activation or engagement of endogenous or infused T cells and/or other immune effector cells. Symptoms can be progressive, always include fever at the onset, and may include hypotension, capillary leak (hypoxia), and end-organ dysfunction (Lee *et al.*, 2019). CRS has been well documented with chimeric antigen receptor T-cell therapies and bispecific T-cell engager antibody therapies but has also

been reported with immunotherapies that target PD-1 or PD-L1 (Rotz *et al.*, 2017; Adashek and Feldman 2019) including atezolizumab.

There may be significant overlap in signs and symptoms of IRRs and CRS, and in recognition of the challenges in clinically distinguishing between the two, consolidated guidelines for medical management of IRRs and CRS are provided in the table below.

#### Management Guidelines for Infusion-Related Reactions and Cytokine-Release Syndrome

Event	Management
Grade 1 a Fever b with or without constitutional symptoms	
 
• Immediately interrupt infusion.
 
• Upon symptom resolution, wait 30 minutes and then restart infusion at half the rate being given at the time of event onset.
 
• If the infusion is tolerated at the reduced rate for 30 minutes, the infusion rate may be increased to the original rate.
 
• If symptoms recur, discontinue infusion of this dose.
 
• Administer symptomatic treatment,c including maintenance of IV fluids for hydration.
 
• In case of rapid decline or prolonged CRS (> 2 days) or in patients with significant symptoms and/or comorbidities, consider managing as per Grade 2.
 
• For subsequent infusions, consider administration of oral premedication with antihistamines, anti-pyretics, and/or analgesics, and monitor closely for IRRs and/or CRS.
 

Grade 2 a Fever b with hypotension not requiring vasopressors and/or Hypoxia requiring low-flow oxygen d by nasal cannula or blow-by	
 
• Immediately interrupt atezolizumab infusion.
 
• Upon symptom resolution, wait for 30 minutes and then restart infusion at half the rate being given at the time of event onset.
 
• If symptoms recur, discontinue infusion of this dose.
 
• Administer symptomatic treatment.c
 
• For hypotension, administer IV fluid bolus as needed.
 
• Monitor cardiopulmonary and other organ function closely (in the ICU, if appropriate). Administer IV fluids as clinically indicated and manage constitutional symptoms and organ toxicities as per institutional practice.
 
• Rule out other inflammatory conditions that can mimic CRS (e.g., sepsis). If no improvement within 24 hours, initiate workup and assess for signs and symptoms of HLH or MAS.
 
• Consider IV corticosteroids (e.g., methylprednisolone 2 mg/kg/day or dexamethasone 10 mg every 6 hours).
 
• Consider anti-cytokine therapy.c
 
• Consider hospitalization until complete resolution of symptoms. If no improvement within 24 hours, manage as per Grade 3, that is, hospitalize patient (monitoring in the ICU is recommended), permanently discontinue atezolizumab.
 
• If symptoms resolve to Grade 1 or better for 3 consecutive days, the next dose of atezolizumab may be administered. For subsequent infusions, consider administration of oral premedication with antihistamines, anti-pyretics, and/or analgesics and monitor closely for IRRs and/or CRS.
 
• If symptoms do not resolve to Grade 1 or better for 3 consecutive days, contact the Principal Investigator.
 

Grade 3 a Fever b with	
 
• Permanently discontinue atezolizumab.
 
• Administer symptomatic treatment.c
 
• For hypotension, administer IV fluid bolus and vasopressor as needed.
 

hypotension requiring a vasopressor (with or without vasopressin) and/or Hypoxia requiring high-flow oxygen d by nasal cannula, face mask, non-rebreather mask, or venturi mask	
 
• Monitor cardiopulmonary and other organ function closely; monitoring in the ICU is recommended. Administer IV fluids as clinically indicated and manage constitutional symptoms and organ toxicities as per institutional practice.
 
• Rule out other inflammatory conditions that can mimic CRS (e.g., sepsis). If no improvement within 24 hours, initiate workup and assess for signs and symptoms of HLH or MAS.
 
• Administer IV corticosteroids (e.g., methylprednisolone 2 mg/kg/day or dexamethasone 10 mg every 6 hours).
 
• Consider anti-cytokine therapy.c
 
• Hospitalize patient until complete resolution of symptoms. If no improvement within 24 hours, manage as per Grade 4, that is, admit patient to ICU and initiate hemodynamic monitoring, mechanical ventilation, and/or IV fluids and vasopressors as needed; for patients who are refractory to anti-cytokine therapy, experimental treatments may be considered at the discretion of the investigator.
 

Grade 4a  Fever b with hypotension requiring multiple vasopressors (excluding vasopressin) and/or  Hypoxia requiring oxygen by positive pressure ( e.g. , CPAP, BiPAP, intubation and mechanical ventilation)	
 
• Permanently discontinue atezolizumab.
 
• Administer symptomatic treatment.c
 
• Admit patient to ICU and initiate hemodynamic monitoring, mechanical ventilation, and/or IV fluids and vasopressors as needed. Monitor other organ function closely. Manage constitutional symptoms and organ toxicities as per institutional practice.
 
• Rule out other inflammatory conditions that can mimic CRS (e.g., sepsis). If no improvement within 24 hours, initiate workup and assess for signs and symptoms of HLH or MAS.
 
• Administer IV corticosteroids (e.g., methylprednisolone 2 mg/kg/day or dexamethasone 10 mg every 6 hours).
 
• Consider anti-cytokine therapy.c For patients who are refractory to anti-cytokine therapy, experimental treatmentsf may be considered at the discretion of the investigator.
 
• Hospitalize patient until complete resolution of symptoms.
 

ASTCT= American Society for Transplantation and Cellular Therapy; BiPAP= bi-level positive airway pressure; CAR= chimeric antigen receptor; CPAP= continuous positive airway pressure; CRS= cytokine-release syndrome; HLH= hemophagocytic lymphohistiocytosis; IRR = infusion-related reaction; MAS= macrophage activation syndrome.

**Note:** The management guidelines have been adapted from NCCN guidelines for management of CAR T-cell-related toxicities (Version 2.2019).

- Grading system for management guidelines is based on ASTCT consensus grading for CRS. NCI CTCAE (version as specified in the protocol) should be used when reporting severity of IRRs, CRS, or organ toxicities associated with CRS on the Adverse Event eCRF. Organ toxicities associated with CRS should not influence overall CRS grading.
- Fever is defined as temperature  $\geq 38^{\circ}\text{C}$  not attributable to any other cause. In patients who develop CRS and then receive anti-pyretic, anti-cytokine, or corticosteroid therapy, fever is no longer required when subsequently determining event severity (grade). In this case, the grade is driven by the presence of hypotension and/or hypoxia.
- Symptomatic treatment may include oral or IV antihistamines, anti-pyretics, analgesics, bronchodilators, and/or oxygen. For bronchospasm, urticaria, or dyspnea, additional treatment may be administered as per institutional practice.
- Low flow is defined as oxygen delivered at  $\leq 6$  L/min, and high flow is defined as oxygen delivered at  $>6$  L/min.

- e. There are case reports where anti-cytokine therapy has been used for treatment of CRS with immune checkpoint inhibitors (Rotz et al. 2017; Adashek and Feldman 2019), but data are limited, and the role of such treatment in the setting of antibody-associated CRS has not been established.
- f. Refer to Riegler et al. for information on experimental treatments for CRS.

### Pancreatic events

Symptoms of abdominal pain associated with elevations of amylase and lipase, suggestive of pancreatitis, have been associated with the administration of atezolizumab. The differential diagnosis of acute abdominal pain should include pancreatitis. Appropriate workup should include an evaluation for ductal obstruction, as well as serum amylase and lipase tests. Management guidelines for pancreatic events, including pancreatitis, are provided in the table below.

Event	Management
Amylase and/or lipase elevation, Grade 2	
Amylase and/or lipase <math>>1.5\text{--}2.0 \times \text{ULN}</math>:
 
 
Continue atezolizumab.
 
Monitor amylase and lipase weekly.
 
For prolonged elevation (e.g., <math>>3</math> weeks), consider treatment with corticosteroids equivalent to 10 mg/day oral prednisone.
 
 
Asymptomatic with amylase and/or lipase <math>>2.0\text{--}5.0 \times \text{ULN}</math>:
 
 
Treat as a Grade 3 event.
 

Amylase and/or lipase elevation, Grade 3 or 4	
 
Withhold atezolizumab for up to 12 weeks after event onset.a
 
Refer patient to GI specialist.
 
Monitor amylase and lipase every other day.
 
If no improvement, consider treatment with corticosteroids equivalent to 1–2 mg/kg/day oral prednisone.
 
If event resolves to Grade 1 or better, resume atezolizumab.b
 
If event does not resolve to Grade 1 or better while withholding atezolizumab, permanently discontinue atezolizumab.c
 
For recurrent events, permanently discontinue atezolizumab.
 

Immune-related pancreatitis, Grade 2 or 3	
 
Withhold atezolizumab for up to 12 weeks after event onset.a
 
Refer patient to GI specialist.
 
Initiate treatment with corticosteroids equivalent to 1–2 mg/kg/day IV methylprednisolone and convert to 1–2 mg/kg/day oral prednisone or equivalent upon improvement.
 
If event resolves to Grade 1 or better, resume atezolizumab.b
 
If event does not resolve to Grade 1 or better while withholding atezolizumab, permanently discontinue atezolizumab.
 
For recurrent events, permanently discontinue atezolizumab.
 

Immune-related pancreatitis, Grade 4	
 
Permanently discontinue atezolizumab.
 
Refer patient to GI specialist.
 

Event	Management
	
 
Initiate treatment with corticosteroids equivalent to 1–2 mg/kg/day IV methylprednisolone and convert to 1–2 mg/kg/day oral prednisone or equivalent upon improvement.
 
If event does not improve within 48 hours after initiating corticosteroids, consider adding an immunosuppressive agent.
 
If event resolves to Grade 1 or better, taper corticosteroids over <math>\geq 1</math> month.
 

a Atezolizumab may be withheld for a longer period of time (i.e.,  $>12$  weeks after event onset) to allow for corticosteroids (if initiated) to be reduced to the equivalent of  $\leq 10$  mg/day oral prednisone. The acceptable length of the extended period of time must be determined by the investigator.

b If corticosteroids have been initiated, they must be tapered over  $\geq 1$  month to the equivalent of  $\leq 10$  mg/day oral prednisone before atezolizumab can be resumed.

#### Dermatologic events

Treatment-emergent rash has been associated with atezolizumab. The majority of cases of rash were mild in severity and self-limited, with or without pruritus. A dermatologist should evaluate persistent and/or severe rash or pruritus. Although uncommon, cases of severe cutaneous adverse reactions such as Stevens-Johnson syndrome and toxic epidermal necrolysis have been reported with atezolizumab. A biopsy should be considered unless contraindicated. Management guidelines for dermatologic events are provided in the table below.

Event	Management
Dermatologic event, Grade 1	
 
Continue atezolizumab.
 
Consider treatment with topical corticosteroids and/or other symptomatic therapy (e.g., antihistamines).
 

Dermatologic event, Grade 2	
 
Continue atezolizumab.
 
Consider patient referral to dermatologist for evaluation and if indicated, biopsy.
 
Initiate treatment with topical corticosteroids.
 
Consider treatment with higher-potency topical corticosteroids if event does not improve.
 

Dermatologic event, Grade 3	
 
Withhold atezolizumab for up to 12 weeks after event onset. a
 
Refer patient to dermatologist for evaluation and if indicated, biopsy.
 
Initiate treatment with corticosteroids equivalent to 10 mg/day oral prednisone, increasing dose to 1-2 mg/kg/day if event does not improve within 48-72 hours.
 
If event resolves to Grade 1 or better, resume atezolizumab. b
 
If event does not resolve to Grade 1 or better while withholding atezolizumab, permanently discontinue atezolizumab.
 

Dermatologic event, Grade 4	
 
Permanently discontinue atezolizumab.
 

Event	Management
Stevens-Johnson syndrome or toxic epidermal necrolysis (any grade)	Additional guidance for Stevens-Johnson syndrome or toxic epidermal necrolysis: 
 
• Withhold atezolizumab for suspected Stevens-Johnson syndrome or toxic epidermal necrolysis.
 
• Confirm diagnosis by referring patient to a specialist (dermatologist, ophthalmologist, or urologist as relevant) for evaluation and, if indicated, biopsy.
 
• Follow the applicable treatment and management guidelines above.
 
• If Stevens-Johnson syndrome or toxic epidermal necrolysis is confirmed, permanently discontinue atezolizumab.
 

a Atezolizumab may be withheld for a longer period of time (i.e., >12 weeks after event onset) to allow for corticosteroids (if initiated) to be reduced to the equivalent of ≤10 mg/day oral prednisone. The acceptable length of the extended period of time must be determined by the investigator. b If corticosteroids have been initiated, they must be tapered over ≥1 month to the equivalent of ≤10 mg/day oral prednisone before atezolizumab can be resumed.	

### Neurologic disorders

Myasthenia gravis and Guillain-Barré syndrome have been observed with single agent atezolizumab. Patients may present with signs and symptoms of sensory and/or motor neuropathy. Diagnostic work-up is essential for an accurate characterization to differentiate between alternative etiologies. Management guidelines for neurologic disorders, and specific guidelines for myelitis, are provided in the table below.

Event	Management
Immune-mediated neuropathy, Grade 1	
 
• Continue atezolizumab.
 
• Investigate etiology.
 
• Any cranial nerve disorder (including facial paresis) should be managed as per Grade 2 management guidelines below.
 

Immune-mediated neuropathy, including facial paresis, Grade 2	
 
• Withhold atezolizumab for up to 12 weeks after event onset. a
 
• Investigate etiology and refer patient to neurologist.
 
• Initiate treatment as per institutional guidelines.
 
• For general immune-mediated neuropathy:               
 
○ If event resolves to Grade 1 or better, resume atezolizumab. b
 
○ If event does not resolve to Grade 1 or better while withholding atezolizumab, permanently discontinue atezolizumab. c
 
 
 
• For facial paresis:               
 
○ If event resolves fully, resume atezolizumab. b
 
○ If event does not resolve fully while withholding atezolizumab, permanently discontinue atezolizumab. c
 
 
 

Immune-mediated neuropathy, including facial paresis, Grade 3 or 4	
 
• Permanently discontinue atezolizumab. c
 
• Refer patient to neurologist.
 
• Initiate treatment as per institutional guidelines.
 

Event	Management
Myasthenia gravis and Guillain-Barré syndrome (any grade)	
 
• Permanently discontinue atezolizumab.c
 
• Refer patient to neurologist.
 
• Initiate treatment as per institutional guidelines.
 
• Consider initiation of corticosteroids equivalent to 1–2 mg/kg/day oral or IV prednisone.
 

a Atezolizumab may be withheld for a longer period of time (*i.e.*, >12 weeks after event onset) to allow for corticosteroids (if initiated) to be reduced to the equivalent of ≤10 mg/day oral prednisone. The acceptable length of the extended period of time must be based on an assessment of benefit–risk by the investigator and in alignment with the protocol requirements for the duration of treatment and documented by the investigator.

b If corticosteroids have been initiated, they must be tapered over ≥1 month to the equivalent of ≤10 mg/day oral prednisone before atezolizumab can be resumed.

c Resumption of atezolizumab may be considered in patients who are deriving benefit and have fully recovered from the immune-mediated event. The decision to re–challenge patients with atezolizumab should be based on investigator's assessment of benefit–risk and documented by the investigator (or an appropriate delegate).

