**8.2.2 Dose Modifications for Atezolizumab**

Administration of atezolizumab will be performed in a setting with emergency medical facilities and staff who are trained to monitor for and respond to medical emergencies.

Premedication is not permitted for the first dose of atezolizumab. Premedication with antihistamines or antipyretics/analgesics (e.g., acetaminophen) may be administered for subsequent infusions at the discretion of the treating physician. The management of Infusion Related Reactions will be according to severity as follows:

- In the event that a patient experiences a Grade 1 Infusion Related Reaction during Cycle 1, the infusion rate should be reduced to half the rate being given at the time of event onset. Once the event has resolved, the investigator should wait for 30 minutes while delivering the infusion at the reduced rate. If tolerated, the infusion rate may then be increased to the original rate.
- In the event that a patient experiences a Grade 2 Infusion Related Reaction, or flushing, fever, or throat pain, the infusion should be immediately interrupted and the patient should receive aggressive symptomatic treatment. The infusion should be restarted only after the symptoms have adequately resolved to baseline grade. The infusion rate at restart should be half of the infusion rate that was in progress at the time of the onset of the Infusion Related Reaction. For subsequent infusions, administer oral premedication with antihistamine and anti-pyretic and monitor closely for Infusion Related Reactions.
- For Grade 3 or 4 Infusion Related Reactions, the infusion should be stopped immediately, and aggressive resuscitation and supportive measures should be initiated (e.g., oral or IV antihistamine, anti-pyretic, glucocorticoids, epinephrine, bronchodilators, oxygen). Atezolizumab should be permanently discontinued. Resumption of atezolizumab may be considered in patients who are deriving benefit and have fully recovered from the immune-related event; retreatment requires consultation with, and consent of, the trial Principal Investigator (PI).

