**General AE Management and Dose Modification Guidelines**

There will be no dose reduction for atezolizumab in this study.

Patients may temporarily suspend study treatment for up to 84 days (12 weeks) beyond the scheduled date of delayed infusion if study drug-related toxicity requiring dose suspension is experienced. If atezolizumab is held because of AEs for 84 days beyond the scheduled date of infusion, the patient will be discontinued from atezolizumab and will be followed for safety and efficacy as specified in this protocol. If the AE resolves within 84 days and the patient is receiving corticosteroid therapy for the event, atezolizumab may be held for longer than 84 days (up to 4 weeks) in order to allow tapering of the steroid dose to  $\leq 10$  mg oral prednisone or equivalent.

Dose interruptions for reasons other than toxicity, such as surgical procedures, may be allowed. The acceptable length of interruption will be at the discretion of the study PI in consultation with CTEP.

The primary approach to grade 1 to 2 irAEs is supportive and symptomatic care with continued treatment with atezolizumab; for higher-grade irAEs, atezolizumab should be withheld and oral and/or parenteral steroids administered. Recurrent grade 2 irAEs may also mandate withholding atezolizumab or the use of steroids. Assessment of the benefit risk balance should be made by the investigator, with consideration of the totality of information as it pertains to the nature of the toxicity and the degree of clinical benefit a given patient may be experiencing prior to further administration of atezolizumab. Atezolizumab should be permanently discontinued in patients with life threatening irAEs.

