#### Pulmonary events

Dyspnea, cough, fatigue, hypoxia, pneumonitis, and pulmonary infiltrates have been associated with the administration of atezolizumab. Patients will be assessed for pulmonary signs and symptoms throughout the study and will have computed tomography (CT) scans of the chest performed at every tumor assessment.

All pulmonary events should be thoroughly evaluated for other commonly reported etiologies such as pneumonia or other infection, lymphangitic carcinomatosis, pulmonary embolism, heart failure, chronic obstructive pulmonary disease, or pulmonary hypertension. Management guidelines for pulmonary events are provided in the table below.

Event	Management
Pulmonary event, Grade 1	
 
Continue atezolizumab and monitor closely.
 
Re-evaluate on serial imaging.
 
Consider patient referral to pulmonary specialist.
 

Pulmonary event, Grade 2	
 
Withhold atezolizumab for up to 12 weeks after event onset.a
 
Refer patient to pulmonary and infectious disease specialists and consider bronchoscopy or BAL.
 
Initiate treatment with corticosteroids equivalent to 1–2 mg/kg/day oral prednisone.
 
If event resolves to Grade 1 or better, resume atezolizumab.b
 
If event does not resolve to Grade 1 or better while withholding atezolizumab, permanently discontinue atezolizumab.
 
For recurrent events, treat as a Grade 3 or 4 event.
 

Pulmonary event, Grade 3 or 4	
 
Permanently discontinue atezolizumab.
 
Bronchoscopy or BAL is recommended.
 
Initiate treatment with corticosteroids equivalent to 1–2 mg/kg/day oral prednisone.
 
If event does not improve within 48 hours after initiating corticosteroids, consider adding an immunosuppressive agent.
 
If event resolves to Grade 1 or better, taper corticosteroids over <math>\geq 1</math> month.
 

BAL bronchoscopic alveolar lavage

a Atezolizumab may be withheld for a longer period of time (*i.e.*, 12 weeks after event onset) to allow for corticosteroids (if initiated) to be reduced to the equivalent of  $\leq 10$  mg/day oral prednisone. The acceptable length of the extended period of time must be determined by the investigator and the Medical Monitor.

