Symptomatic hyperthyroidism	
 
Withhold atezolizumab.
 
Initiate treatment with anti-thyroid drug such as methimazole or carbimazole as needed.
 
Consider patient referral to endocrinologist.
 
Resume atezolizumab when symptoms are controlled and thyroid function is improving.
 
Permanently discontinue atezolizumab.
 

Symptomatic adrenal insufficiency, Grade 2–4	
 
Withhold atezolizumab for up to 12 weeks after event onset.a
 
Refer patient to endocrinologist.
 
Perform appropriate imaging.
 
Initiate treatment with corticosteroids equivalent to 1–2 mg/kg/day IV methylprednisolone and convert to 1–2 mg/kg/day oral prednisone or equivalent upon improvement.
 
If event resolves to Grade 1 or better and patient is stable on replacement therapy, resume atezolizumab.b
 
If event does not resolve to Grade 1 or better or patient is not stable on replacement therapy while withholding atezolizumab, permanently discontinue atezolizumab.
 

Hyperglycemia, Grade 1 or 2	
 
Continue atezolizumab.
 

Event	Management
	
 
Investigate for diabetes. If patient has Type 1 diabetes, treat as a Grade 3 event. If patient does not have Type 1 diabetes, treat as per institutional guidelines.
 
Monitor for glucose control.
 

Hyperglycemia, Grade 3 or 4	
 
Withhold atezolizumab.
 
Initiate treatment with insulin.
 
Monitor for glucose control.
 
Consider referral to endocrinologist, particularly if patient is deemed to have atezolizumab-induced diabetes; if so, obtain C-peptide level paired with glucose, autoantibody levels (e.g. GAD65, islet cell autoantibodies), and hemoglobin A1C level.
 
If patient is found to have diabetic ketoacidosis or hyperglycemic hyperosmolar syndrome, treat as per institutional guidelines with appropriate management and laboratory values (e.g. anion gap, ketones, blood pH, etc.) reported.
 
Resume atezolizumab when symptoms resolve and glucose levels are stable.
 

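### Footnote c to the neurologic table allows atezolizumab re-challenge without excluding life-threatening events or requiring trial PI consent

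*Combined protocol and SAP*

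**What the plan says.** All the relevant text is in the combined protocol and SAP, Section 8.2.2 (Dose Modifications for Atezolizumab).

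- **Neurologic disorders table.** The order to discontinue permanently carries marker c in the row "Immune-mediated neuropathy, including facial paresis, Grade 3 or 4" and in the row for myasthenia gravis and Guillain-Barré syndrome, which covers every grade. Marker c also appears in the Grade 2 row, for neuropathy or facial paresis that does not resolve during the hold.
- **Footnote c.** "Resumption of atezolizumab may be considered in patients who are deriving benefit and have fully recovered from the immune-mediated event". The decision rests on the investigator's benefit-risk assessment, which the investigator or a delegate must document.
- **General AE Management and Dose Modification Guidelines.** "Atezolizumab should be permanently discontinued in patients with life threatening irAEs". No exception is given.
- **Opening text of 8.2.2, Grade 3 or 4 infusion-related reactions.** Permanent discontinuation, followed by almost the same permission to resume, but with the condition that "retreatment requires consultation with, and consent of, the trial Principal Investigator (PI").
- **Later table for infusion-related reactions and cytokine-release syndrome.** Permanent discontinuation at Grades 3 and 4, with no way back to treatment.

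**The concern.** Footnote c qualifies the discontinuation order itself, in rows that include Grade 4 events and all grades of two conditions that can be grave. Section 9.4 marks Guillain-Barré syndrome, myasthenia gravis and peripheral neuropathy with a note that checkpoint inhibition can produce severe and even fatal immune-mediated events. A patient who recovers fully from a life-threatening episode meets the footnote's recovery condition but falls under the general guideline's order to stop for good. One site may treat the footnote as a specific exception to the general rule. Another may treat the general rule as an absolute bar. Each could cite the protocol.

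The patients have had complete resection and have no evidence of residual disease (Section 3.2.2). The footnote's condition that the patient be benefiting therefore cannot be checked through tumour response in an individual. In practice the gate is full recovery plus one investigator's judgement. What is at stake is re-exposure, as adjuvant treatment, of a patient who has already had a serious neurologic reaction.

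**Working it through.** No arithmetic applies. The check is a comparison of the provisions in Section 8.2.2.

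| Provision | Event | Route back to atezolizumab | Who must agree | Life-threatening events excluded? |
|---|---|---|---|---|
| Neurologic table, footnote c | Neuropathy Grade 3 or 4; myasthenia gravis or Guillain-Barré syndrome, any grade; unresolved Grade 2 neuropathy or facial paresis | Yes, after full recovery and if benefiting | Site investigator, documented | Not stated |
| General AE guideline | Any life-threatening immune-related event | None stated | Not applicable | This is the exclusion |
| Opening text, infusion reactions | Grade 3 or 4 | Yes, same two conditions | Trial PI must be consulted and must consent | Not stated |
| Infusion reaction and cytokine-release table | Grade 3 or 4 | None | Not applicable | Not applicable |

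1. **Overlap.** The first two rows can cover the same patient. An any-grade row for Guillain-Barré syndrome necessarily includes its life-threatening forms. For neuropathy the overlap is less exact, because the table does not define Grade 4. The only neuropathy scale printed (Section 8.2.1.4, for oxaliplatin) has a Grade 4 that covers disabling as well as life-threatening symptoms.
2. **Precedence.** Neither the footnote nor the general guideline refers to the other, and no other text ranks them. The German appendix (AIO-GSA 1.3, item 5) stops treatment for events that meet the Section 8.2 criteria, which leads back to the section containing footnote c.
3. **Approval.** The first and third rows share the same two clinical conditions. They differ in that the third adds the trial PI's consent. The fourth row contradicts the third, so the comparison shows that the permission was drafted with a consent step in one place and without it in another. It does not show a settled protocol standard.
4. **Awareness.** Sections 9.3 and 9.3.1 require 24-hour notification of life-threatening events to the NCI, with notice to the Study Chair and the IRB. The study leadership would therefore know of the event. That reporting duty gives no veto over a later re-challenge.
5. **Statistical reach.** Efficacy is analysed by randomised arm whatever treatment was received (Section 13.0). Re-challenge or its refusal changes neither the analysis set nor the one-sided 0.025 level, nor the requirement of 165 events.

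**The case against.** The best reply is that both texts can be followed together. Footnote c is permissive and does not claim to override the general guideline, so a careful site would not re-challenge after a life-threatening event. A reader might infer that the protocol positively authorises such re-challenge. The documents do not support that. They leave the order of the two rules unstated, which is a smaller fault.

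A reader might also infer that second approval is the protocol's norm and that footnote c departs from it. The pulmonary footnote does say "The acceptable length of the extended period of time must be determined by the investigator and the Medical Monitor", and for interruptions unrelated to toxicity, "The acceptable length of interruption will be at the discretion of the study PI in consultation with CTEP". But the parallel extended-hold footnote appears in ten tables, and in nine of them the investigator alone decides or documents the length. The pulmonary one is the outlier. The general guideline also gives the benefit-risk assessment to the investigator. This objection stands, and only the infusion-reaction wording is a fair comparator for re-challenge.

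Nor can footnote c be called the sole exception among the permanent-discontinuation rows. Marker c also appears, without a printed footnote, on unresolved Grade 3 or 4 amylase or lipase elevation. The protocol also allows return after events as severe as Grade 4 elsewhere. For adrenal insufficiency of Grade 2 to 4 it says "If event resolves to Grade 1 or better and patient is stable on replacement therapy, resume atezolizumab", although that row orders a hold and not permanent discontinuation.

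Other limits exist. The 84-day cap on holds may narrow the footnote's use, though its application after permanent discontinuation is not stated. At German sites, the sponsor's opinion that an event contraindicates dosing stops treatment (AIO-GSA 1.3, item 2). The Investigator's Brochure, to which 8.2.2 refers for managing these events, was not available. These points reduce the concern. None of them says which rule prevails or supplies a consent step across all sites.

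**Conclusion.** The point holds as a minor patient-safety wording issue. Footnote c permits re-challenge on the site investigator's documented judgement, does not exclude life-threatening events, does not state its relation to the general guideline, and lacks the consent step attached to nearly identical wording in the same section.

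The number of patients concerned is unknown and may be zero. A reader might try to derive a ceiling from Section 9.4, which lists each of these terms as rare but serious, below 3% of 3097 patients. Applied to 350 adults in Arm 1, 0.03 × 350 = 10.5. That is an expected count at the category limit, for all grades of one term, and not an upper bound. Section 9.4 also warns that combination treatment may behave differently. Life-threatening cases with full recovery are an unknown part of any such count.

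The point has practical effect only while atezolizumab is being given. German last treatment was planned for February 2023 (AIO-GSA 1.5), and the status elsewhere is not stated. The August 30, 2024 date in Section 9.3.1 belongs to the reporting requirements and is no evidence of continuing dosing. Alpha, power and the disease-free survival analysis are unaffected.

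**What to change.** If any dosing continues, add two sentences to footnote c: *This footnote does not apply to life-threatening events, for which atezolizumab is permanently discontinued (see General AE Management). Any other re-challenge under this footnote requires that the trial PI be consulted and give consent.* Keep the existing conditions on recovery, benefit and documentation.

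The change adds no study procedures. Its cost falls on very few patients: those who recover from a life-threatening event lose re-challenge, and the others, including those with unresolved Grade 2 neuropathy who later recover fully, need the PI's agreement first.
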